4.3 JUSTIFICATION FOR INTERVENTION

In order to ensure the needed variation, it is important that participants engage heavily with the work offered and that those offered less work do not compensate heavily outside the study. To ensure this is the case, we will conduct the study in the lean-season leading into the harvest, when cash is very much needed (consumption often dips heavily during this time) and work availability is quite low (typically just a few days per month). While we are relatively confident that limited work is available outside of the study given previous research in this area, we have planned for a year of piloting to allow us to evaluate whether the work provided is sufficiently attractive to ensure high and consistent engagement with the work offered.

4.4 END-OF-STUDY DEFINITION

A participant is considered to have completed the study if he or she has completed the baseline assessment and the endline assessment.

The end of the study is defined as completion of the 1-month follow-up assessment shown in the Schedule of Activities (SoA), **Section 1.3**.

5 STUDY POPULATION

5.1 INCLUSION CRITERIA

The study will take place in communities/districts around Tamale in the Northern Region of Ghana. The randomization will be conducted to ensure that there will only be one participant per household. Households will be randomly selected to partake in a screening survey in 135 villages to identify eligible participants. Individuals will be eligible if and only if:

- 1) They are between the ages of 18 and 65. Only individuals of legal age to work will be enrolled to ensure compliance with local laws. Further, restricting the sample to adults (18 and over) ensures all participants are able to provide informed consent and are in compliance with local labor regulations. Enrollment is limited to those under 65 given that the nature of the work may be physically taxing and generate additional risk for these individuals.
- 2) The participant is female. This restriction is needed for two reasons. First, the study requires high take-up of the work offered in order to provide interpretable results and women are less likely to have other work obligations that would generate partial participation. Second, gender norms in the area make the work provided (sewing) relevant to women but not men.
- 3) To guarantee that the data collection is feasible within short time windows, large households, with many working adults, will not be eligible to participate in the study. The exact limit of this cutoff will be determined using pilot data.
- 4) All participants must provide informed consent.

5.2 EXCLUSION CRITERIA

We will exclude women who are pregnant as pregnancy and the post-partum period are often associated with depression unrelated to one's work environment (and hence less likely to be impacted by our treatments). However, no participants will be dropped from the study if they become pregnant during their participation and wish to continue.

5.3 LIFESTYLE CONSIDERATIONS

N/A

5.4 SCREEN FAILURES

Screen failures are defined as participants who do not meet the inclusion and exclusion criteria defined above or those who decline to participate after completing the informed consent procedure. These individuals will be thanked for their time, but will have no further contact with the study. They will not be rescreened at a later date as all study enrollment happens in a limited time window driven by the study design.

5.5 STRATEGIES FOR RECRUITMENT AND RETENTION

We expect to screen roughly 10,000 households to reach our enrollment target of 2,267 participants. Households to be screened will be determined by a random sampling procedure within the targeted villages until the target number of households is reached. The target number of households per village will be a function of the village size, to ensure a relatively sparse randomization. These interviews will be conducted in person as in-person data collection will result in more accurate screening data and avoid any concerns around unreliable cell service and limited literacy. All of these households will be located in the vicinity of Tamale, Ghana. Local enumerators who are fluent in the local dialects and familiar with these areas will be enlisted to undertake this screening. Enumerators will not work after dark for their safety in traveling. To ensure participant safety, the interview will take place in a location of the participant's choice near or in their home and the study team will conduct back-checks and flag any discrepancies from protocols for review with a supervisor.

The screening will produce a household roster to identity potentially eligible individuals within the household. Consistent with the inclusion and exclusion criteria of the study, these individuals will be non-pregnant women between 18-65 years old living in (relatively) small households.

This process will result in roughly 2,267 African women between the ages of 18-65 being enrolled into the study (see inclusion/exclusion criteria for justifications for age restrictions).

The household screening survey used to determine eligibility will be conducted over the course of approximately 4-5 weeks in the spring of 2025. We will then enroll all participants in the study in 2-4 weeks in late March to early May of 2025. The pilot study will be conducted in the late spring/early summer of 2024.

The study will include multiple survey rounds. Participants will be provided with incentives (cash or in-kind gifts, to be determined via piloting) for their participation in the surveys. This compensation is intended to be similar to or slightly above (25%) compensation for their time in the local labor market. In addition, this data collection will be made as convenient as possible via collection by phone or in which the surveyor travels to meet the participant at their house. To date, our implementation partners (IPA Ghana) have had excellent retention in studies in this area, often exceeding 90%. All survey payments will be made directly to the respondent.

Importantly, participants in the treatment groups are also compensated for their time working as a part of the study. The compensation is roughly 25-50% above the local minimum wage, an amount which we believe compensates them sufficiently for their time while not providing undo inducement. Payments for work will be made three times throughout each two-week period as the work is completed.

Because participants are economically disadvantaged and some may not literate, we will ensure comprehension of the informed consent by reading all documents to the potential participant and will ensure comprehension of the key points via comprehension questions and checks.

6 STUDY INTERVENTION(S) OR EXPERIMENTAL MANIPULATION(S)

6.1 STUDY INTERVENTION(S) OR EXPERIMENTAL MANIPULATION(S) ADMINISTRATION

6.1.1 STUDY INTERVENTION OR EXPERIMENTAL MANIPULATION DESCRIPTION

The poor are known to suffer disproportionally from poor mental and physical health. Many causes for these disparities have been considered, including low income. Yet, poor families' incomes are not only low, but also often unstable and unpredictable (Collins et al. 2009). Income instability creates uncertainty about whether they will be able to safeguard their future wellbeing: Will they have enough money to put food on the table? To pay for rent? To pay for a doctor's visit? (Jolliffe and Ziliak 2008; Bhattacharya et al. 2004) The allostatic load framework posits that, if uncertainty (of any type) is not resolved, prolonged activation of physiological stress responses will cause "wear and tear" on the body, heightening risks of cardiovascular disease and of agerelated metabolic diseases, promoting cognitive decline and dementia, and accelerating cellular aging (Peters et al. 2017). Income instability could therefore increase the rate of aging among the poor and contribute to disparities in physical and psychological health.

In order to parse the impacts of volatility and uncertainty on mental health, we must vary both the variance in income and what is know about the expected path of income among participants while holding constant the mean expected income.

To accomplish this, all participants are enrolled in the study for 6 two-week "periods" (3 months) and a short follow-up survey one month after the end of the active study period. During the study period participants are randomly divided into the following four groups.

1) *The Control Arm.* The Control arm will not be hired by the cash-for-work program but will be surveyed.

2) *The Stable Income Arm*. The Stable Income arm will work the same number of hours (36) and earn the same amount (108 GHS) every period.

3) *The Predictable Instability Arm*. The hours and earnings of the Predictable Instability arm will vary over time. In three periods, the participant will work longer hours (60) and will earn more (180 GHS). In the remaining three periods, she will work fewer hours (12) and will earn less (36 GHS). Crucially, she will be able to predict all swings in her study earnings in the future—i.e., she will know her hours and earnings in each future period.

4) *The Unpredictable Instability Arm.* The hours and earnings of the Unpredictable Instability arm will vary unpredictably over time. In any given period, there will be a 50% chance that she works longer hours (60) and earns more (180 GHS) and a 50% chance that she works fewer hours (12) and earns less (36 GHS).

Common to all treated arms: Importantly, participants are not required to complete all of the work that they are offered. As a result, Predictable Volatility and Unpredictable Instability participants will have the option to implement, if they wish, a fixed work schedule with non-varying earnings. If in periods when offered 60 hours, the participant voluntarily chooses to work just 12 hours, she can ensure to always work 12 hours and always be paid GHS 36 (per period). Similarly, any other number of days within the maximum number of days offered is also allowed without penalty. All wages will be paid daily for work that is completed. As such, there is no penalty for non-attendance at any level.

We believe the effects of income volatility and uncertainty on mental health are likely to operate through economic channels. Hence, the study will collect data on key economic indicators such as household consumption, savings, and debt.

The targeted clinical endpoints are as noted in Section 3.

6.1.2 ADMINISTRATION AND/OR DOSING

The study operates in 6 2-week "periods." Within each period, treated participants are provided with materials to complete their work in the first few days of the period. They then follow a schedule of collections and payments over the next ten days. Finally, in the final 4 days of the period, all participants including the control, complete their survey. A dedicated staff will provide the materials, collect the completed work, and make payments for the completed work. These staff are hired via PAS, a local NGO which has engaged in a similar intervention in the past. A separate staff will conduct surveys. These staff are hired via IPA Ghana, a non-profit research organization with extensive experience in conducting surveys in the field and by phone.

The participants will compete the work (i.e. the intervention) in their homes. The intervention is considered "full dose" if the individual completes at least some work in each period. As participants are paid for each unit of work completed, we are able to track the "dosage" for each individual in great detail.

The work from home design and sparse randomization (roughly 1% of the village population) is intended to minimize participant interactions, though participants are in no way prevented from interacting with each other as they usually might in the village.

6.2 FIDELITY

6.2.1 INTERVENTIONIST TRAINING AND TRACKING

It is important to have consistent administration of the study interventions. To ensure this is the case, we have:

- 1) Found an implementation partner with previous experience in very similar work in a previous academic study
- 2) Generate the work plans using a fixed set of schedules that are easy to follow and can be monitored via the data on material drop-off and pick-up/payments. This will allow us to quickly catch and address any deviations from the intended plan. This data is updated daily at the end of the day and code is run to flag any deviations. Supervisors then check in with their supervisees about these deviations and make a plan to correct any deviations. Additionally, study participants have access to a "hotline" to report any concerns about deviations from expected schedules or protocols.
- 3) Planned for a pilot to ensure that operations are running smoothly prior to launching the study at scale.

We do not anticipate any variability in delivery, with the exception of random shocks (e.g. heavy rainfall that delays the delivery of materials) which will likely impact all arms equally. We have

generated contingency plans to mitigate the effects of such shocks (e.g. each participant is given additional material at the beginning of the study to be used in such cases).

Changes in the structure of the experimental arms over the study will be tracked via two data sources:

- 1) Data on the completion of the offered work, as described above
- 2) Data on the completion of the bi-weekly surveys.

Given the high retention of participants of studies with similar interventions in this region with our implementing partner, we expect that retention in the study will be over 90% in all arms. Should retention be significantly lower than expected or imbalanced across study arms, we should identify this concern in the pilot and will be able to adjust protocols (e.g. to increase convenience), compensation, or timelines (i.e how close to harvest the study is conducted) to address these concerns.

6.3 MEASURES TO MINIMIZE BIAS: RANDOMIZATION AND BLINDING

We will recruit 2,267 participants, randomly assigning 400 to the Control, 400 to the Stable Income, 400 to the Predictable Volatility, and 1,067 to the Unpredictable Instability arm. Among those in the Unpredictable Instability arm, we expect 1/3 to end the study with the same average earnings as those in the Stable or Predictable volatility arm. Roughly 1/3 will earn more overall and roughly 1/3 will earn less overall, given the randomized draws. Participants are not (and cannot be) blind to their condition. The randomization will be conducted using Stata or R following the completion of the screening process. Because not all individuals selected via screening will consent, we will identify "backup" participants in each wave of enrollment to reach our target enrollments. We will stratify the randomization within village to improve power.

2,267 Participants					
400 Control	400 Stable Income	400 Predictable Volatility	1,067 Unpredictable Instability		

The period-by-period randomization for the amount of work received by each participant in the Unpredictable Instability arm will follow the protocol described in Section 4.1.

6.4 STUDY INTERVENTION/EXPERIMENTAL MANIPULATION ADHERENCE

The participant's adherence to study procedures among treated participants will be tracked using the same datasets used to track fidelity to the intervention because this dataset captures not only that the material was provided to the participant, but also what work the participant has completed using that material. This dataset, generated from the electronic surveying records, allows us to track that engagement with the work provided is high and consistent across all arms of the study. Data is uploaded and a monitoring script is run daily.

However, participants will be retained in the study (and all corresponding survey activities) regardless of their engagement with the work provided as long as they wish to do so.

Adherence to surveys will also be tracked via the electronic surveying software used. We will generate bi-weekly reports (the same frequency as the surveying) on survey engagement across study arms.

We will work to survey all participants originally recruited, including any who drop out of the program, and expect a high tracking rate because: (i) the endline will be conducted only three months post-baseline; (ii) we will stay in frequent contact through the phone surveys; and (iii) IPA Ghana has a strong follow-up protocol and rates (over 94% (Amadu et al. 2018; Wolf et al. 2018)). We will estimate bounds if response rates vary across arms. Given IPAs performance on previous lean season surveys (when respondents typically have time), we anticipate 5% attrition across all arms.

6.5 CONCOMITANT THERAPY N/A

6.5.1 RESCUE THERAPY

No rescue medications will be used. However, appropriate referral procedures are in place to provide counseling and support to those experiencing extreme mental distress. See section 8.2 for additional details.

7 STUDY INTERVENTION/EXPERIMENTAL MANIPULATION DISCONTINUATION AND PARTICIPANT DISCONTINUATION/WITHDRAWAL

7.1 DISCONTINUATION OF STUDY INTERVENTION/EXPERIMENTAL MANIPULATION

No interim analysis is planned because the study is minimal risk (i.e. participants are always able to opt out of the work offered, neither the work nor the surveys are riskier than everyday activities). Given this, there are no study stopping rules for the study as a whole. Similarly, there are no criteria for individual discontinuation, should the individual wish to continue.

However, we do anticipate that individuals may need to discontinue participation at times and may wish to restart later. For example, the study takes place in an area with high disease burden. Hence, an individual who falls ill with a fever may wish to stop participation for a few weeks to recover and then rejoin.

We do not anticipate any SAE, AE, or UP in the administration of the study given that the work (sewing bags) is low-risk and the surveys are no more than minimal risk. Further, because the income generated by the study can be very valuable, both in material and psychological terms, we do not plan to involuntarily remove anyone from the study as the result of an adverse event unless they would like to discontinue. Should an individual wish to discontinue, we would collect any remaining sewing, make the corresponding payments, and thank the participant for their participation. If the individual wishes to restart at a later date (while the study was still ongoing),

they would be allowed to do so and would simply rejoin as soon as logistically possible (typically within one week).

Should an unanticipated AEs or SEA arise that was determined to be study related (to be determined by the site investigator and the PI following the procedures in the data safety and monitoring plan), this would be reported to the relevant IRB within 48 hours and to the DSMB members at the next DSMB meeting. For AEs and SEAs related to health, participants will be referred to the closest government health post or hospital, depending on the severity of the event. The costs of transportation for AEs and SEAs considered related or potentially related to study participation will be covered by the study.

If they so wish, their participation in the study would be halted until they felt able and willing to rejoin.

Regardless of whether a participant discontinues engagement with the intervention, they will be asked if they are able and willing to continue with the ongoing surveys. These surveys are an important component of our participant safety protocols as they allow us to screen and refer participants with significant signs of psychological distress (see Section 8.2). Should a participant not be available at their home for the in-person survey, we will attempt to contact them to complete a shortened version of the study instrument via phone. Notably, we collect multiple forms of contact information at enrollment to allow us to track participants who have changed their phone numbers.

7.2 PARTICIPANT DISCONTINUATION/WITHDRAWAL FROM THE STUDY

Participation may be discontinued at the participant's request for voluntary withdrawal from the study. The reason for discontinuation will be recorded in the participant's tracking form. The PI will not discontinue any participants for non-compliance, but if a participant is deceased, they will be removed from the study. Additionally, the study will continue to try and contact a participant if they have not explicitly asked us to discontinue such contact, though this contact may be shifted to telephonic communication if the participant has relocated a significant distance from their original home. Participants who discontinue their participation or remain unreachable will not be replaced. However, subjects who sign the informed consent form and are randomized but do not receive their treatment assignment information or study intervention may be replaced. Power calculations have accounted for potential loss to follow up.

7.3 LOST TO FOLLOW-UP

A participant will be considered lost to follow-up if he or she fails to complete the endline survey or at least 3 of the phone surveys. If a participant is unavailable or not present at their home at the time of the endline survey, 2 additional attempts will be made to contact the individual and schedule a new time for the survey. If they are unable to complete the survey in person at their home, we will ask if they are willing to take a shortened form of the survey by telephone. All phone-based surveys must be conducted prior to the beginning of the following period. Hence, if the participant remains unreachable after 4 call attempts during this window, no further attempts will be made to recontact them for that survey round. However, the standard protocol will be followed at the next round of data collection in two weeks.

8 STUDY ASSESSMENTS AND PROCEDURES

8.1 ENDPOINT AND OTHER NON-SAFETY ASSESSMENTS

Endpoints

Surveys will be conducted at baseline and every two weeks throughout the study as well as once roughly one month following the study. The baseline and "endline" (following period 6) are conducted in-person and are longer, typically taking about 2.5 hours. All other surveys are conducted by phone, typically taking under 30 minutes. These surveys will be used to collect our primary and secondary outcomes, described in section 3 as well as measures of channels (primarily economic outcomes), and demographics. These outcomes include:

Mental Health Outcomes:

- Anxiety
 - Abbreviated Version of General Anxiety Disorder (GAD-2)
 - General Anxiety Disorder-7 (GAD-7)
- Depression
 - Abbreviated Version of Patient Health Questionnaire (PHQ-2)
 - Patient Health Questionnaire-8 (PHQ-8)
- Stress
 - Abbreviated Version of Cohen's Perceived Stress Scale (PSS-4)
 - Cohen's Perceived Stress Scale (PSS)
 - Cortisol (Participants will be asked to provide a small sample of hair to measure cortisol levels. There is no penalty for declining this request. The hair collected will be from the approximately 2 cm below the cranial bone and cutting off 2-3 strands of hair, following the hair collection study protocol developed by the Biomarker Network. The hair samples will be collected at the participant's home and analyzed in a single laboratory.)
- Wellbeing
 - Diener's Satisfaction with Life Scale
- Worry
 - Penn State Worry Questionnaire (PSWQ)

To ensure that the measures are well-understood, the translations will be validated, by a local mental health expert, [name] of the University of Ghana. Further, to ensure consistency in the translation and understanding, the survey items will be pre-recorded and played via the tablet used to conduct the survey. The enumerator will then simply key in the response provided

by the participant. Scoring of the scales above follows the standardized approaches/scoring of these measures which are all common in the existing mental health literature.

Physical health related outcomes:

- Blood pressure
- Weight
- Dietary diversity and sufficiency

Enumerators will receive extensive training in the collection of blood pressure and weight measures.

Measures of channels, such as:

- Consumption
- Labor supplied outside of the study
- Gifts/transfers
- Debts/savings
- Assets/wealth

Demographics (abbreviated list):

- Age
- Size of household
- Education
- Marital status

Screening process

The study will take place in communities/districts around Tamale in the Northern Region of Ghana. Surveys will be conducted in 135 villages to identify eligible participants. Local enumerators who are fluent in the local dialects and familiar with these areas will be enlisted to undertake this screening. These individuals are not doctors and do not have any medical training, but none of the screening criteria are medical in nature.

The screening will produce a household roster to identity potentially eligible individuals within the household. Consistent with the inclusion and exclusion criteria of the study, these individuals will be non-pregnant women between 18-65 years old living in (relatively) small households.

This process will result in roughly 2,267 African women between the ages of 18-65 being enrolled into the study (see inclusion/exclusion criteria for justifications for age restrictions).

The household surveys used to determine eligibility will be conducted over the course of approximately 4-5 weeks in the spring of 2025. We will then enroll all participants in the study in 2-4 weeks in late March to early May of 2025. Pilot participants will be enrolled in late April and May of 2024.

Additional details

As the study is not clinical in nature, no clinical care will be provided.

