9.2 SAMPLE SIZE DETERMINATION

Given IPAs' performance on similar previous surveys during the lean season (when respondents are relatively available), we assume a uniform 5% attrition across all arms.

We will recruit 2,267 participants. 1,067 will be assigned to the Unpredictable Instability arm and 400 to each one of the other three study arms. About 37.5% of the Unpredictable Instability arm (i.e., 400 individuals) are expected to have Neutral 4-period schedules, such that the estimation of the effect of ex-ante income uncertainty corresponds to a randomized controlled trial with a sample size of 760 (95% of 800) equally split between "treatment" and "control". For a two-tailed test with 0.05 significance level and 0.8 power, the minimum detectable effect (MDE) is 0.2 of a standard deviation (SD) for each primary outcome (calculations done in Stata). These effect sizes are consistent with those found in the literature on the effects of cash transfers in low-income settings (e.g., Haushofer & Shapiro, 2016 & 2018; McIntosh & Zeitlin, 2020). Similarly, the MDE for the effect of predictable income volatility is also 0.2 SD. The estimation of the effect of income risk, which corresponds to RCT where 72.7% of the 1,394 (95% of 1,467) participants are assigned to the treatment condition, has an MDE of 0.17 SD. The estimation of the effect of income realizations has an MDE of 0.19 SD if those with unlucky and lucky schedules are grouped together and of 0.23 SD if they are each compared separately to those with Neutral schedules. For panel data analyses, standard errors will be clustered at the individual level (the unit of randomization) (Abadie et al. 2017). These are conservative estimates that consider data from the follow-up survey only; they ignore that we will have baseline measures of all outcomes of interest, which should substantially reduce MDEs, and that we will have repeated measures of most outcomes. In addition to an index of mental health, given the rapid evolution of multiple hypothesis testing techniques, will we use state of the art techniques to adjust for multiple hypothesis testing.

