9.4 STATISTICAL ANALYSES

9.4.1 GENERAL APPROACH

To study the effects of uncertainty, we will compare the outcomes of participants assigned to the Unpredictable Instability arm to the outcomes of participants assigned to the Predictable Instability arm, while holding the payment schedule constant. Similarly, to study the effects of predictable income volatility, we will compare the outcomes of participants assigned to the Predictable Instability arm to the outcomes of participants assigned to the Stable Income arm. Finally, we will estimate the effects of a stable income by comparing the outcomes of participants assigned to the Control arm.

For each of the individual outcomes, the primary regression model will be:

$$Y_{it} = \lambda_0 + \sum_{\{k=1\}}^3 \lambda_1^k T_i^k + \lambda_2 X_i + \lambda_3 Y_{i0} + \gamma_t + \epsilon_{it}.$$

where *i* indexes the individual; Y_i is individual *i*'s outcome in the post-treatment period *t*; T_i^k is an indicator for treatment arm k; X_i is a vector of individual-level controls (e.g., age); Y_{i0} is the dependent variable at baseline; and; ϵ_i is the error term. Period fixed effects (γ_t) are also included to control for period effects. The analysis considers treatment assignment as the independent variable, regardless of compliance (i.e., intent-to-treat). We utilize an ANCOVA regression model. Standard errors are clustered by individual. λ_1 are the key coefficients of interest and can be interpreted as the causal effect of each treatment relative to the control group. Additional comparisons between treatments will be conducted to parse the impacts of predictable and unpredictable volatility. Also, to study if outcomes fluctuate together with income, we will compare participants from a given arm with different current study earnings (but who had identical earnings in the past). Given the rapid evolution of multiple hypothesis testing.

A pre-analysis plan will be registered after the pilot but prior to the main study with any updates to this analysis plan based on learnings from the pilot.

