9.4.2 ANALYSIS OF THE PRIMARY ENDPOINT(S)

We will use the standardized scoring approaches to all mental health outcomes, including any reversals of scale items as needed. These measures are repeated as described in the timelines previously.

ANCOVA regressions, as outlined in section 9.4.1 above, will be run to analyze the differences between experimental arms. Standard errors will be clustered by individual in all panel regressions. Results will be presented in a regression table with point estimates and standard errors. The regressions will be intention to treat (ITT) with all available data. Data will be cleaned to winsorize outliers, but no imputation will be conducted. If attrition is imbalanced, bounding exercises will be conducted. Given the rapid evolution of multiple hypothesis testing techniques, will we use state of the art techniques to adjust for multiple hypothesis testing.

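### As written, the cortisol ANCOVA leaves out women who give endline hair but no baseline hair; a missing-baseline rule would keep them

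*Combined protocol and SAP*

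**What the plan says.** - **Endpoint.** Section 3 lists stress measured by cortisol among the five primary endpoints.
- **Collection.** Section 8.1 says cortisol comes from hair taken at the participant's home. Of the request for a sample it says: "There is no penalty for declining this request". No expected completion or refusal rate is given anywhere.
- **Model.** Section 9.4.1 specifies an ANCOVA in which Y_i0 "is the dependent variable at baseline".
- **Missing data.** Section 9.4.2 says: "Data will be cleaned to winsorize outliers, but no imputation will be conducted". It also says the regressions are intention-to-treat on all available data, with bounding if attrition is imbalanced. No section says what happens when a baseline value is missing.
- **Power.** Section 9.2 says "we assume a uniform 5% attrition across all arms" and gives an MDE of 0.2 SD "for each primary outcome (calculations done in Stata"). It calls its figures conservative because they use follow-up data only and take no credit for baseline or repeated measures.
- **Timing.** Section 4.1 says participants learn their arm after consent and the baseline survey.

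**The concern.** A regression cannot use a row in which a regressor is missing. With the baseline value in the model and no imputation allowed, a woman who declines hair at baseline but gives it at endline has an observed primary outcome that the planned model cannot use. Most other primary outcomes are survey answers or simple measurements taken at the baseline visit, so few baseline values should be missing. Hair is the one primary measure that the plan expressly invites women to decline.

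What is at stake is precision on the only biomarker of stress, and an analyst's choice left open on a primary endpoint. If the rule is settled after the data are seen, dropping or keeping these women becomes a discretionary step.

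**Working it through.** **Inputs from Section 9.2.** Two-sided 0.05, power 0.8, and 760 women split equally after 5% attrition, so 380 per arm (the ex-ante uncertainty comparison).

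**Assumptions, not in the documents.** Refusal r at each visit (10%, 20%, 30%), baseline-endline correlation rho (0.3, 0.5), and refusal unrelated to cortisol level.

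**Step 1. Reproduce the stated figure.** With SD = 1, MDE = (1.960 + 0.842) × sqrt(2/n) = 2.8016 × sqrt(2/380) = 0.2032. This rounds to the stated 0.2, so the plan's arithmetic is right on its own inputs. As a cross-check, the income-risk comparison (380 v 1,014) gives 0.1685, against the stated 0.17.

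**Step 2. Drop women without baseline hair (the plan as written), refusals independent.** Women with both samples number n = 380(1 − r)² per arm, and MDE = 2.8016 × sqrt(2(1 − rho²)/n). At r = 20% and rho = 0.5, n = 380 × 0.64 = 243.2 and MDE = 2.8016 × sqrt(1.5/243.2) = 0.220.

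**Step 3. Keep them, using a constant and a missing-baseline indicator.** Women with endline hair number n = 380(1 − r) per arm. The residual variance is a mixture: 1 − rho² for those with baseline hair and 1 for those without. So MDE = 2.8016 × sqrt(2[(1 − r)(1 − rho²) + r]/n). At r = 20% and rho = 0.5, n = 304, the bracket is 0.8 × 0.75 + 0.2 = 0.80, and MDE = 2.8016 × sqrt(1.6/304) = 0.203. Dropping costs (0.75/243.2)/(0.80/304) = 1.17, or 17% more variance.

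**Step 4. The same women refuse both times.** Everyone with endline hair also has baseline hair, so n = 304 either way and MDE = 2.8016 × sqrt(1.5/304) = 0.197. The rule neither gains nor costs anything.

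| rho | r | Independent, dropped | Independent, kept | Same women refuse (either rule) |
|---|---|---|---|---|
| 0.3 | 10% | 0.215 | 0.205 | 0.204 |
| 0.3 | 20% | 0.242 | 0.219 | 0.217 |
| 0.3 | 30% | 0.277 | 0.235 | 0.232 |
| 0.5 | 10% | 0.196 | 0.189 | 0.186 |
| 0.5 | 20% | 0.220 | 0.203 | 0.197 |
| 0.5 | 30% | 0.251 | 0.221 | 0.210 |

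**Step 5. When does the cortisol MDE, with women dropped, exceed 0.2032?** If the same women refuse, when r > rho²: 9% at rho 0.3 and 25% at rho 0.5. If refusals are independent, when (1 − r)² < 1 − rho², that is r > 1 − sqrt(1 − rho²): about 5% and 13%. Whether cortisol ends above or below the stated figure therefore depends on quantities the documents do not give.

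**The case against.** A reader might infer that the 0.2 SD MDE is wrong for cortisol. The documents do not support that. The figure reproduces, and Section 9.2 says openly that it takes no credit for baseline adjustment. That adjustment can more than offset the loss: at rho 0.5, 10% independent refusal still gives 0.196 with women dropped. It is also tempting to put the reduced count of 243 per arm into the unadjusted formula, but that count arises only because the baseline covariate is in the model. An unadjusted comparison would not need baseline hair, so that calculation charges the covariate's cost and ignores its benefit.

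Three further points are fair:
- Willingness to give hair may well persist within a woman, which moves the truth towards the no-gain case.
- Dropping is the default result of the written model rather than a stated rule. Because Section 9.4.2 speaks of all available data, it is not a plain breach of the intention-to-treat population in Section 9.3.
- The pre-analysis plan due after the pilot could settle the matter, although nothing commits it to do so.

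What does not stand is relying on the plan's conservatism alone. Section 9.2 counts on baseline measures of all outcomes, yet baseline hair may be declined. It also counts on repeated measures of most outcomes, but hair taken at home cannot come from a phone round, even though the Section 1.3 schedule lists cortisol in the block marked for short phone surveys. The shortened telephone endline in Section 7.3 would likewise yield a survey without hair. Section 7.2 says power accounts for loss to follow-up, which is not the same as sample refusal.

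**Conclusion.** The point holds as one about precision and specification. Followed literally, the plan discards endline cortisol from women without baseline hair. Under the assumed 20% independent refusal and correlation of 0.5, this moves the MDE from 0.203 to 0.220 SD. Across the assumed range with independent refusal, the difference runs from 0.007 SD (rho 0.5, r 10%) to 0.042 SD (rho 0.3, r 30%). It is zero if the same women refuse both times.

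It is not a finding of bias between arms. Baseline refusal comes before a woman knows her arm, so it costs precision and possibly generalisability. This rests on the staff who collect baseline hair also not acting on the allocation, which Section 4.1 states only for participants. Endline refusal comes after assignment and could differ by arm. The missing-baseline rule does not address that, and the bounds in Section 9.4.2 must cover it.

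The 0.2 SD figure is not shown to be wrong. Applying it to cortisol is unsupported until hair completion is allowed for.

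**What to change.** - **Section 9.4.2.** State that every participant with a post-treatment value enters the regression; that a missing baseline covariate is set to a constant, with an indicator for missing baseline added; and that the ban on imputation applies to outcomes only. The last part is needed because filling in a constant is itself a form of imputation. The rule can apply to every outcome.
- **Section 9.4.2, bounds.** Say that the imbalance check and bounds for cortisol are based on endline hair completion by arm, not on survey completion.
- **Section 9.2.** Add a cortisol MDE under the planned ANCOVA that allows for expected hair completion at each visit, for example at the rate seen in the 400-participant pilot.

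The cost is a sentence or two in Section 9.4.2, one indicator variable and one restated MDE. The pre-analysis plan, to be registered after the pilot and before the main study, is a natural place to fix all three. No change to data collection is needed.
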